### 3.3 Inferential Analyses

No formal hypothesis testing is planned.

Descriptive statistics will be used to summarize the safety and immunogenicity data.

### **3.4 Multiple Comparisons and Multiplicity Adjustments.**

Not applicable for this study.

### **3.5 Handling of Missing Data**

All collected and derived data will be included in the subject data listings. No imputations will be made for missing or incomplete data unless otherwise stated.

For the classification of Treatment emergent adverse event (TEAE) and Concomitant medication, the following will be applied in the following order:

- a. If all dates/times (start and stop) are missing, the event/medication will automatically be classified as a TEAE/Concomitant medication.
- b. For AEs with a missing start date/time, if the event end date/time is prior to first study drug administration, the event will not be classified as a TEAE.
- c. If only the AE start year/ medication end year is present and is the same or is after the first study drug administration year unit, the event/medication will be classified as a TEAE/Concomitant medication.
- d. If the AE start month and year/medication end month and year are present and are the same or after the first study drug administration month and year units, the event/medication will be classified as a TEAE/Concomitant medication.

#### For Immunogenicity quantitative data:

Immunological parameters below the Lower Limit Of Quantification (LLOQ) or the Limit Of Detection (LOD) (when available) will be imputed by half the lower limit of quantification or half the limit of detection for the descriptive summary. Immunological parameters above the Upper Limit of Quantification (ULOQ) will be imputed by multiplying by 2.

Such substitutions will be clearly documented in the footnotes of relevant outputs.

Missing immunogenicity results will not be replaced nor extrapolated.

### Conversion of categorical values

In some instances, continuous variables are expressed as a range (i.e., < 10). In such cases, values may be converted to the range boundary (upper or lower limit as applicable). As an example, a value of <10 may be converted to 10. Such substitutions will be clearly documented in the footnotes of relevant outputs.

### **3.6 Coding of Events and Medications**

Medical history and AE verbatim terms will be coded using the Medical Dictionary for Regulatory Activities (MedDRA®) using the 26.1 available at the time of study commencement. Terms will be coded to the full MedDRA® hierarchy, but the system organ class (SOC) and preferred terms (PT) will be of primary interest for the analysis.

Prior and concomitant medications will be coded using the World Health Organization Drug Dictionary using the 26.1 available at the time of study commencement. Medications will be mapped to the full WHO-DD Anatomical Therapeutic Chemical (ATC) class hierarchy, but PTs will be of primary interest in this analysis.

### **3.7 Treatment arms**

The following Treatment labels will be used for Summary Tables and Figures and Listings for the randomized population, the detailed dose of the treatment received will be given in footnote:

- Arm 1 (Medium dose)
- Arm 2 (High dose)
- Arm 3 (Placebo)
- Arm 1 + Arm 2
- Overall

#### **4. ANALYSIS POPULATIONS**

In this study 5 analysis populations are defined: Screened Analysis Set (ScS), Intent to Treat (ITT), Per Protocol Analysis Set (PPS), Safety Analysis Set (SAF) and Immunogenicity Analysis Set (IS).

Furthermore, any additional exploratory analysis not identified in the SAP will be identified in the final CSR as exploratory post hoc analyses, including analyses for additional study populations or subgroups of interest.

##### **4.1 Population Descriptions**

###### **4.1.1 Screened Analysis Set (ScS)**

All subjects who enter screening (assigned a screening number).

###### **4.1.2 Intent to Treat (ITT)**

All subjects who are randomized. The analyses using ITT will be based upon the randomization group allocated.

###### **4.1.3 Per Protocol Analysis Set (PPS)**

All subjects in the ITT set who receive one dose and who have not violated any inclusion/exclusion criteria and / or deviated in a way that could influence their Immunogenicity assessments.

###### **4.1.4 Safety Analysis Set (SAF)**

All randomized subjects who receive at least 1 dose of the study drug. Subjects will be analyzed according to the treatment (vaccine) they actually received. All safety analyses will be conducted based on the Safety set.

###### **4.1.5 Immunogenicity Analysis Set (IS)**

All randomized subjects who receive at least 1 dose of the study drug and have at least one valid immunogenicity result after Day 1. Subjects will be analyzed according to the treatment (vaccine) they actually received. All immunogenicity analyses will be conducted based on the Immunogenicity set.

## **5. SUBJECT DISPOSITION AND ANALYSIS POPULATIONS**

Subject disposition and analysis population analysis will be based on ITT population. Subject disposition and analysis populations will be summarized descriptively as described in section 3.1 (categorical descriptive analysis).

### **5.1.1 Subject Disposition**

Subject disposition will include the number of subjects who completed the study active period and treatment as planned, subjects withdrawn from the study active period and treatment, as well as the primary reason for early termination.

### **5.1.2 Analysis Populations**

The number of subjects included in each study populations will be summarized descriptively. In addition, the inclusion of each subject into/from each of the defined analysis populations will be presented in the by-subject data listings.

**6. PROTOCOL DEVIATIONS**

Protocol deviations will be presented for each subject in the by-subject data listings.

Prior to database lock, all protocol deviations will be reviewed by medical monitors and assigned a status of Important if qualifying as such.

Protocol deviations and important protocol deviations will be categorized as noted in the Project Management Plan version 1.0 dated 30-AUG-2023.

## **7. DEMOGRAPHIC AND BASELINE INFORMATION**

Demographic and baseline information analysis will be based on the Safety analysis set (SAF). Demographic and baseline information will be summarized descriptively as described in [section 3.1](#) (Continuous/ Categorical data)

### **7.1 Demographics**

The following demographic parameters will be analyzed:

#### Continuous descriptive analysis:

- Age (years)
- Height (cm)
- Weight (kg)
- BMI (kg/m^2)

#### Categorical descriptive analysis:

- Sex
- Childbearing Potential
- Race
- Ethnicity

All demographic parameters collected will be presented, for each treatment arm, in the by-subject data listings.

### **7.2 Medical /Surgical history**

Medical / Surgical history will be coded using the latest MedDRA® version. All medical/surgical history as collected will be presented in the by-subject data listings and will be summarized by System Organ Class (SOC) and Preferred Term (PT) as described in [section 3.1](#) (categorical data).

Subject who had multiple medical histories will be counted once in the specific category (SOC/ PT). SOC and PTs will be presented alphabetically. In addition to the summaries by the coded terms, the number of subjects with at least one medical history during the study will be presented.

All data collected will be presented, for each treatment arm, in the by-subject data listings.

### **7.3 Serology**

Hepatitis B Surface Antigen (HBsAg), Hepatitis C Virus and Human Immunodeficiency Virus (HIV) results will be presented, for each treatment arm, in the by-subject data listings.

### **7.4 Urine Drug Screen**

Urine Drug Test results will be presented, for each treatment arm, in the by-subject data listings.

### **7.5 Alcohol Test**

Alcohol Test results obtained will be presented, for each treatment arm, in the by-subject data listings.

**8. TREATMENT EXPOSURE**

All study drug administration information (study drug administered (Yes/No), reason not administered, date and time of administration, dose format, study drug given as per protocol (Yes/No) and reason not given will be presented, for each treatment arm, in the by-subject data listings.

## 9. PRIOR AND CONCOMITANT MEDICATIONS

Concomitant medications will be summarized by Anatomical Therapeutic Chemical (ATC) class Level 3 and PT as noted in [section 3.1](#) (categorical descriptive analysis) for Safety Analysis Set. Subjects who used the same medication on multiple occasions will only be counted once in the specific category (PT). PTs will be sorted alphabetically. In addition to the summaries by the coded terms, the number of subjects who used at least one concomitant medication during the study will be presented.

Prior and concomitant medications will be presented in the by-subject data listings.

## **10. PHARMACOKINETICS**

No PK Analysis is planned for this study.

## **11. PHARMACODYNAMICS**

No pharmacodynamic (PD) analysis is planned for this study.

**12. EFFICACY**

The exploratory efficacy analysis to assess the occurrence of acute gastroenteritis will be evaluated during the study period. The count and percentage of subject will be provided on safety population.

### 13. SAFETY

Safety endpoints will be analyzed using the SAF. Solicited Symptoms of Reactogenicity, unsolicited AEs, SAEs, and vital signs will be summarized descriptively by treatment arm (two active vaccine arms and placebo) and study day as described in [section 3.1](#) (Categorical/Continuous).

Analyses will be performed for the total set (active vs. placebo).

SAEs will be categorized according to MedDRA® terms. The safety analyses are based on the safety set. Subjects will be summarized by vaccine arm and placebo according to the study drug they actually received. Missing reactogenicity Diary data will not be imputed; missing TEAE dates will be handled according to the rules determined in the SAP.

#### 13.1 Solicited Symptoms of Reactogenicity

Solicited symptoms are predefined signs and symptoms of reactogenicity for which the subject is specifically questioned, and which are noted by the subject in their Solicited Symptom Diary, including:

- Fever (any temperature 100.4°F or higher)
- Headache
- Myalgia (muscle pain)
- Abdominal Pain
- Anorexia (defined and not eating)
- Nausea
- Vomiting
- Diarrhoea
- Malaise/Fatigue

Subjects will utilize a Solicited Symptom Diary issued on the day of the vaccination to record solicited symptom daily for one week (from Day 1 to Day 8) following that administration. After Day 8 solicited symptoms will be captured as unsolicited Adverse Events as described in [section 13.2](#) with Day 8 as date of onset.

The count and percentage of subjects and the associated Clopper-Pearson 95% CIs reporting at least one solicited symptom during 8 days after vaccine administration (the 8 days include Day 1) will be summarized for each dose and presented by severity and cumulatively across severity levels as listed below:

- Grade 1 Solicited Symptoms
- Grade 2 Solicited Symptoms
- Grade 3 Solicited Symptoms
- Grade 4 Solicited Symptoms

where Grade 1 is mild, Grade 2 is moderate, Grade 3 is Severe, and Grade 4 is Potentially Life threatening as defined in Table 10 “Grading of Solicited Symptoms of Reactogenicity”.

Missing reactogenicity Diary data will not be imputed.

All the solicited symptoms collected during the active period of the study will also be presented for each treatment arm, study day, by severity in by-subject listing.

#### 13.2 Unsolicited AE from Day 1 to Day 29 Post-Vaccination

An unsolicited AE is an observed AE that does not fulfill the conditions prelisted in the eCRF in terms of diagnosis and/or onset window post-vaccination; this also includes progression of chronic diseases. Unsolicited AEs includes both serious (SAEs) and non-serious unsolicited AE.

The unsolicited AE summaries will include:

- Overall summary of Unsolicited TEAEs that included at least one:
  - Unsolicited TEAEs

- Grade  $\geq 3$  Unsolicited TEAEs
- Related Unsolicited TEAEs
- Grade  $\geq 3$  and Related Unsolicited TEAEs
- Serious TEAE
- Adverse Events of Special Interest (AESIs)
- New Onsets of Chronic Illness (NOCIs)
- Unsolicited TEAEs lead to study discontinuation
- Unsolicited TEAEs result in death
- Unsolicited TEAEs summary by SOC and PT
- Grade  $\geq 3$  Unsolicited TEAEs summary by SOC and PT
- Related Unsolicited TEAEs summary by SOC and PT

The Grading of Severity of an TEAE is defined as:

- Grade 1 = mild
- Grade 2 = moderate
- Grade 3 = severe +/- life threatening

In the summary tables, the total number of subjects having reported at least one unsolicited AE with the proportion and the associated Clopper-Pearson 95% CIs, as well as the total number of AEs reported and the duration will be provided for each treatment arm. For example, the tables will state that X (%) subjects have reported Y events in the treatment arm A. Then, they will present the details of unsolicited AEs per SOC and PT with the same information: number (%) of subjects and number of events.

In the summary tables, unsolicited AEs will be presented by decreasing frequency of number of subjects with event and total events under “overall” treatment arm within each SOC and then similarly by decreasing frequency of number of subjects with event and total events under “overall” treatment arm within each PT.

Missing unsolicited TEAE dates will be handled according to the rules determined in [section 3.1](#) (Date and time display conventions)

In addition, the duration of unsolicited TEAEs will be evaluated descriptively where subjects without AE are counted as missing.

All the unsolicited AEs collected during the active period of the study will also be provided for each treatment arm, study day, by severity and relationship to the treatment in by-subject listings. Separate listings will be done for subjects with TEAEs leading to study discontinuation, SAEs, AESIs, NOCIs and for Death events.

### 13.3 Serious Adverse Events

In the summary tables, the total number of subjects having reported at least one SAE with the proportion and the total number of SAEs reported will be provided for each treatment arm. For example, the tables will state that X (%) subjects have reported Y events in the treatment arm A. Then, they will present the details of SAEs per SOC and PT with the same information: number (%) of subjects and number of events.

The SAE summaries at Day 365 Post-Vaccination will include:

- SAEs summary by SOC and PT
- SAEs summary by SOC, PT and Severity
- SAEs summary by SOC, PT and Relationship

In the summary tables, SAEs will be presented by decreasing frequency of number of subjects with event and total events under “overall” treatment arm within each SOC and then similarly by decreasing

frequency of number of subjects with event and total events under “overall” treatment arm within each PT.

All SAEs collected during the follow-up period of the study will also be provided for each treatment arm, study day, in duration, by severity and relationship to the treatment in by-subject listings.

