11.4.2 Analysis of the Primary and Secondary Safety End Points

Safety will be summarized for the safety set (active vs. placebo). Solicited Symptoms of Reactogenicity, unsolicited AEs, SAEs, physical examination, and vital signs will be summarized descriptively by treatment group and study visit.

Analyses will be performed for the total set (active vs. placebo). All results will be presented descriptively and summarized by treatment groups.

Endpoint	Statistical Analysis Methods
Primary (measured from Day 1 through Day 29)	
Frequency, duration, and severity of Solicited Symptoms of Reactogenicity (local, systemic) measured daily for 1 week following vaccination.
 
Frequency, duration, and severity of unsolicited AEs, and SAEs through the active period (4 weeks post dose).
 
Descriptive statistics will be provided for each reactogenicity endpoint for each dose. Local reactions and systemic events from Day 1 through Day 8 after each dose will be presented by severity and cumulatively across severity levels. Descriptive summary statistics will include counts and percentages of subjects with the indicated endpoint and the associated Clopper-Pearson 95% CIs.
 
AEs will be categorized according to the Medical Dictionary for Regulatory Activities (MedDRA[®]) terms. Descriptive summary statistics (counts, percentages, and associated Clopper-Pearson 95% CIs) will be provided for any TEAEs for each vaccine group as well as the placebo group. SAEs will be categorized according to MedDRA[®] terms. The safety analyses are based on the safety set. Subjects will be summarized by vaccine group and placebo according to the study drug they actually received. Missing reactogenicity Diary data will not be imputed; missing TEAE dates will be handled according to the rules determined in the SAP.

Secondary (measured through Day 365)	Frequency, duration, and severity of SAEs, AESIs and NOCIs for 1 year following the study drug dose.

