### 2.2.2 Secondary objective(s)

- **Safety**
  - To determine the long-term safety of bivalent GI.1/GII.4 norovirus vaccine through 12 months after the last vaccination.
- **Immunogenicity**
  - To assess the long-term immunogenicity of oral bivalent GI.1/GII.4 norovirus vaccine administration in healthy lactating female participants and most critically, the association with vaccine specific antibody responses in breast milk.

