### 2.3.2 Secondary endpoints

- **Safety**
  - Frequency, duration, and severity of all SAEs, AESIs, and NOCIs through 12 months after last study drug dose
- **Immunogenicity**
  - Serum VP1 specific (GI.1 and GII.4) IgA through 6 months after study drug dose measured by Meso Scale Discovery (MSD) by dose level
    - Geometric mean concentration (GMC) at Day 180
    - Geometric mean fold rise (GMFR) from Day 1 to Day 180
    - The number of subjects in each dose group that had a 2-fold, 3-fold and 4-fold GMC rise or greater in serum VP1 specific IgA (GI.1 and GII.4) between Day 1 and Day 180.
  - Breast Milk VP1 specific (GI.1 and GII.4) IgA through 6 months after study drug dose measured by Meso Scale Discovery (MSD) by dose level
    - Geometric mean concentration (GMC) at Day 60 and Day 180
    - Geometric mean fold rise (GMFR) from Day 1 to Day 60 and from Day 1 to Day 180
  - Serum VP1 specific (GI.1 and GII.4) IgG through 6 months after study drug dose measured by Meso Scale Discovery (MSD) by dose level
    - Geometric mean concentration (GMC) at Day 1, Day 8, Day 29, and Day 180
    - Geometric mean fold rise (GMFR) from Day 1 to Day 8, from Day 1 to Day 29, and from Day 1 to Day 180
    - The number of subjects in each dose group that had a 2-fold, 3-fold and 4-fold GMC rise or greater in serum VP1 specific IgG (GI.1 and GII.4) between Day 1 and any other timepoint.
  - Serum Blocking titers 50 (BT50) (GI.1 and GII.4) through 6 months after study drug dose measured by Histo-blood group antigen (HBGA) assay by dose level
    - Geometric mean titer (GMT) at Day 1 and Day 29
    - Geometric mean fold rise (GMFR) from Day 1 to Day 29,
    - The number of subjects in each dose group that had a 2-fold, 3-fold and 4-fold GMT rise or greater in serum blocking titers 50 (BT50) (GI.1 and GII.4) between Day 1 and any other timepoint.

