## 2.4 Sample Size

A sample size of 76 randomized subjects (30 each in medium and high dose levels and 16 in placebo) is not based on formal statistical testing but rather based on clinical judgement and predicted to yield meaningful safety and immunogenicity results. Placebo was added for safety comparison.

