### **13.4 New Onset of Chronic Illness**

New Onset of Chronic Illness (NOCI) is defined as diagnosis post-enrollment and vaccination of a new medical condition which is chronic in nature, including those potentially controllable by medication (e.g., diabetes, asthma).

In the summary tables, the total number of subjects having reported at least one NOCI with the proportion and the total number of NOCIs reported will be provided for each treatment arm. For example, the tables will state that X (%) subjects have reported Y events in treatment arm A. Then, they will present the details of NOCIs per SOC and PT with the same information: number (%) of subjects and number of events.

The NOCIs summaries at Day 365 Post-Vaccination will include:

- NOCIs summary by SOC and PT
- NOCIs summary by SOC, PT, and Severity
- NOCIs summary by SOC, PT and Relationship

In the summary tables, NOCIs will be presented by decreasing frequency of number of subjects with event and total events under “overall” treatment arm within each SOC and then similarly by decreasing frequency of number of subjects with event and total events under “overall” treatment arm within each PT.

All NOCIs collected during the follow-up period of the study will also be provided, for each treatment arm, study day, in duration, by severity and relationship to the treatment in by-subject listings.

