### **13.5 Adverse Event of Special Interest**

An adverse event of special interest (AESI) (serious or nonserious) is one of scientific and medical concern specific to the Sponsor’s product or program, for which ongoing monitoring and rapid communication by the Investigator to the Sponsor can be appropriate. For this study, AESIs are serious or non-serious adverse events of scientific and medical concern with potential immune-mediated medical conditions as well as events associated with thrombosis and thrombocytopenia as listed in Table 11 in the protocol.

In the summary tables, the total number of subjects having reported at least one AESI with the proportion and the total number of AESIs reported will be provided for each treatment arm. For example, the tables will state that X (%) subjects have reported Y events in treatment arm A. Then, they will present the details of AESIs per SOC and PT with the same information: number (%) of subjects and number of events.

The AESIs summaries at Day 365 Post-Vaccination will include:

- AESIs summary by SOC and PT
- AESIs summary by SOC, PT, and Severity
- AESIs summary by SOC, PT and Relationship

In the summary tables, AESIs will be presented by decreasing frequency of number of subjects with event and total events under “overall” treatment arm within each SOC and then similarly by decreasing frequency of number of subjects with event and total events under “overall” treatment arm within each PT.

All AESIs collected during the follow-up period of the study will also be provided for each treatment arm, study day, in duration, by severity and relationship to the treatment in by-subject listings.

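### The 12-month safety endpoint (SAEs, AESIs, NOCIs) is to be reported as counts and percentages without confidence intervals, and no cumulative Day 1-365 summary is listed

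*SAP*

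**What the plan says.** SAP 2.2.2 sets the secondary safety objective: "To determine the long-term safety of bivalent GI.1/GII.4 norovirus vaccine through 12 months after the last vaccination". The matching endpoint in SAP 2.3.2 is "Frequency, duration, and severity of all SAEs, AESIs, and NOCIs through 12 months after last study drug dose".

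SAP 13.3 to 13.5 describe the summaries, each by treatment arm:

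- SAEs (13.3): "the total number of subjects having reported at least one SAE with the proportion and the total number of SAEs reported will be provided".
- NOCIs (13.4): "the total number of subjects having reported at least one NOCI with the proportion and the total number of NOCIs reported will be provided".
- AESIs (13.5): "the total number of subjects having reported at least one AESI with the proportion and the total number of AESIs reported will be provided".

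Each section adds breakdowns by system organ class and preferred term, severity and relationship, and by-subject listings that include duration. No interval is named.

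The preceding sections differ. SAP 13.1 gives Clopper-Pearson 95% CIs for solicited symptoms. SAP 13.2, for unsolicited AEs from Day 1 to Day 29, reports subjects with "at least one unsolicited AE with the proportion and the associated Clopper-Pearson 95% CIs".

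The rest of the plan does not fill the gap. The remarks on CIs in SAP 3.1 fix decimal places only, and SAP 3.3 plans no hypothesis test. In Protocol 11.4.2 (version 2.0) the row for the secondary endpoint through Day 365 restates the endpoint and names no method.

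SAP 13.3 to 13.5 speak of summaries at Day 365, but the tables listed in SAP 18 (14.3.3.1.7.1-.6, .8.1-.6 and .9.1-.6) cover either Day 1-29 or Day 30-365. None covers Day 1-365.

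**The concern.** These are the rarest and most serious events in the trial, and they make up the whole of the secondary safety endpoint. Where counts are small, the percentage says little: 0 (0.0%) looks the same for 16, 30 or 60 women. An interval tells the reader what a small count has ruled out. The plan supplies one for the commoner, milder, short-term events and leaves it out for the 12-month ones.

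At stake is how a low or zero count will be described in the CSR addendum. Protocol 2.2.3 shows how such a result can be presented: for the earlier boost-schedule study in 30 adults it reports no SAEs, AESIs or NOCIs in safety follow-up and describes the vaccine as safe and generally well tolerated, with no bound. That study had other safety data as well, so this is an illustration of reporting style and not a fault in its conclusion. Its total size equals one dose arm here.

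The split tables add a second difficulty. The endpoint runs through 12 months, but the summaries give two separate windows. A woman with an event in each window is counted once in each table, so the 12-month proportion cannot be obtained by adding them.

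**Working it through.** **Inputs.** Arm sizes come from SAP 2.4: "76 randomized subjects (30 each in medium and high dose levels and 16 in placebo) is not based on formal statistical testing". They add up: 30 + 30 + 16 = 76. The pooled active column (Arm 1 + Arm 2, SAP 3.7) has 30 + 30 = 60. The interval is the exact two-sided Clopper-Pearson 95% interval that the plan already uses. The documents state no precision, power or expected event rate, so there is no planned figure to reproduce.

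**Step 1: zero events.** The lower limit is 0 and the upper limit is 1 − 0.025^(1/n).

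- One dose arm: 1 − 0.025^(1/30) = 11.57%.
- Pooled active: 1 − 0.025^(1/60) = 5.96%.
- Placebo: 1 − 0.025^(1/16) = 20.59%.

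The beta quantile (0.975; 1, n) gives the same values. A one-sided 95% bound, 1 − 0.05^(1/n), would be lower: 9.5% for n=30 and 4.9% for n=60. The rule of three gives 10% and 5%.

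**Step 2: one event.** The upper limit is the 0.975 quantile of Beta(2, n − 1).

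| Group | n | Upper limit, 0 events | Upper limit, 1 event |
|---|---|---|---|
| One dose arm | 30 | 11.6% | 17.2% |
| Pooled active | 60 | 6.0% | 8.9% |
| Placebo | 16 | 20.6% | 30.2% |

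**Step 3: incomplete follow-up.** No dropout figure is given. Assuming 10% to 20% loss by Day 365, a dose arm of 30 falls to 27 or 24. The zero-event upper limit becomes 1 − 0.025^(1/27) = 12.8% or 1 − 0.025^(1/24) = 14.2%.

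**Step 4: how often a real rate would show nothing.** The probability of no event is (1 − p)^n. The range of p is assumed.

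| True 12-month rate | n=30 | n=60 |
|---|---|---|
| 1% | 74.0% | 54.7% |
| 2% | 54.5% | 29.8% |
| 5% | 21.5% | 4.6% |

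These probabilities follow from sample size alone, and printing an interval does not change them. They show why a zero count needs its upper limit beside it.

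**Step 5: why the row must be cumulative.** Suppose a dose arm of 30 has one woman with an SAE in Day 1-29 and one woman with an SAE in Day 30-365. The two tables show 1/30 and 1/30. If it is the same woman, the 12-month figure is 1/30 with interval 0.1% to 17.2%. If they are two women, it is 2/30 with interval 0.8% to 22.1%. An interval column added only to the listed tables would not show which applies.

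**The case against.** The strongest case against acting is that this is a descriptive phase I trial with no hypothesis test, no formal sample-size basis and no safety criterion. Nothing in the plan says that zero events means safe. The counts are also not the only safety evidence: SAEs, AESIs and NOCIs are each assessed for causality (Protocol 8.1), the Safety Monitoring Committee has oversight to Day 365 (10.2), and one treatment-related SAE is enough to be a listed pause or stop trigger (14.1). An exact interval depends only on the count and the denominator, so a reader of a cumulative count could compute it. All of this stands. It makes the point one of reporting: no estimate or decision in the plan changes. It does not explain why the interval is given for short-term events and left out for the 12-month ones.

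Day 1-29 is partly covered. The overall summary in SAP 13.2 has rows for serious TEAEs, AESIs and NOCIs, and its intervals may extend to them. That does not reach Day 30-365 or the full 12 months.

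A reader might also infer that the SAP silently departs from the protocol, because Protocol 11.4.2 says that "Descriptive summary statistics (counts, percentages, and associated Clopper-Pearson 95% CIs) will be provided for any TEAEs" and a post-dose SAE meets the protocol's TEAE definition. The documents do not support this. That sentence stands in the row for the primary endpoints, Day 1 through Day 29, and note g to the Schedule of Activities confines TEAE collection to the active period. The protocol promised no interval for Day 365, so SAP 15 had no omission to disclose.

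**Conclusion.** The point holds as a reporting gap. For SAEs, AESIs and NOCIs through Day 365 the plan gives counts and percentages without confidence intervals and lists no cumulative summary. If no events were seen, rates up to 11.6% per dose arm, 6.0% in pooled active and 20.6% on placebo would remain compatible with the data.

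These limits assume that every randomized woman is dosed and followed to Day 365; losses widen them. They are two-sided 95% limits, the plan's own method, and a one-sided 95% bound for one dose arm would be 9.5%.

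Two stronger readings go beyond the documents. One is that zero events is the likely result. No event rate is given, and over a year SAEs include any inpatient hospitalization and abnormal pregnancy outcomes, while NOCIs include any new chronic condition. The other is that long-term safety will be decided on the counts alone. The plan sets no such rule; it only lacks anything that would show how little a low count excludes. The change is worth making because it costs almost nothing and states the precision of a named secondary endpoint.

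**What to change.** In SAP 13.3, 13.4 and 13.5, add a cumulative Day 1-365 row for subjects with at least one SAE, NOCI or AESI respectively. Give n, % and the Clopper-Pearson 95% CI, shown also when the count is zero, for Arm 1, Arm 2, Arm 1 + Arm 2 and placebo. Add the matching entries to the table list in SAP 18. State that this interval will accompany any 12-month safety statement in the CSR addendum, for example 0/60 with an upper 95% limit of 6.0%.

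The cost is SAP wording and one extra row and column per summary, with a method already specified in SAP 13.1 and 13.2. No new data or participants are needed. The downside is that a zero-event result will read less favourably.
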